## 11.0 Inclusion and Exclusion Criteria

Individuals who have been predicted via an artificial intelligence-intelligence based model to experience a rise in A1C in the near future (90 days) will be approached for recruitment. 36 participants will be recruited from the Children's Mercy Diabetes Center (any clinic or hospital location). Based on preliminary data review of our clinic population, there were at least 81 individuals who met inclusion criteria who were seen in clinic in the month of May 2019 alone. Patients will be randomized to, COIN2DOSE, LOAN2DOSE, or control group using a 1:1:1 randomization scheme.

Inclusion Criteria:

- 1) Aged 12-17.99 years
- 2) The youth must have been diagnosed with T1D for at least 6 months
- 3) The youth must have attended at least 2 routine T1D standard of care visits in the past 12 months

- 4) The youth must be using an insulin delivery device capable of recording, storing, and downloading insulin bolus behaviors (insulin pump or smart Bluetooth insulin pen that can be uploaded to standard clinic upload software).
- 5) The youth must have a current A1C >7.2% and/or be predicted to have a rise in A1C in of 0.3% or higher the next 90 days.
- 6) Not pregnant or planning to become pregnant by self-report.

Exclusion Criteria:

- 1) Participants with any type of diabetes mellitus other than T1D
- 2) Participant has any disease-causing anemia or affecting red blood cell physiology (which would impact A1C)
- 3) Participant has a physical disability, which in the opinion of the investigator would interfere with individual's ability to feed themselves or use one's hands to facilitate eating
- 4) Participants with no internet access or ability to upload device(s) to data aggregation software that is accessible to study team.

For Focus Groups:

Any parent or legal guardian whose child is participating in the study is invited to participate in a focus group discussion.

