## 2.0 Objectives

### 2.1 Primary Objectives

The long-term goal is to develop effective ways to improve glycemic control in youth with T1D. To that end, we propose to specifically evaluate the effectiveness, feasibility, and usability of two new interventions in diabetes care: an economic incentive (COIN2DOSE) and an approach that uses an economic loss aversion (LOAN2DOSE) to promote patient engagement with mealtime insulin dosing behavior. If initially efficacious, our results will serve as the basis for an R01 submission(s) to conduct a fully powered efficacy trial of COIN2DOSE and LOAN2DOSE. This study is significant as omission of mealtime boluses is one of the common reasons for suboptimal diabetes control in youth. This project is highly innovative because it will: 1) target youth who are predicted by artificial intelligence to experience a worsening in glycemic control, 2) use an economic incentive intervention to improve mealtime insulin dosing behavior and 3) use an economic loss aversion to improve mealtime insulin dosing behavior.

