Adolescence is a particularly challenging time for individuals with T1D, with average A1C values that are 5% higher than during other periods of childhood and 14% higher than adults (22) (2). Glycemic control worsens from early childhood through age 16-18 (23). It is critically important to develop interventions to prevent deterioration in glycemic control. High glycemic variability is also associated with increased risk of long-term diabetes complications, such as microalbuminuria (24). Lack of adherence to diabetes treatment plans is one of the main causes of sub-optimal glycemic control (3) (25) (7). A significant part of this non-adherence is omission of insulin for ingested carbohydrates at snacks and meals, both by missing boluses entirely and by inaccurate carbohydrate counting (26) (16) (27) (28) (29). Studies have shown significant underestimation of carbohydrate content in meals of up to 20% (26). Furthermore, greater than 33% of adolescents fail to give insulin for >15% of their meals and snacks (16). Adolescents, on average, miss boluses for meals two times per week (28). In one study, youth who omitted insulin at least one time per week had an A1C of 8.8-9.5%, while those who consistently took meal-time insulin had a significantly lower A1C of 7.8-8.0% (28) (30). This is of great significance as poor glycemic control increases risk of both acute and chronic diabetes related complications (31). Meal bolus alarms on insulin pumps, which alarm at a preset time, lead to transient, modest changes in dosing behavior (32). “Lost focus” has been identified as a significant reason for missed meal-time boluses in adolescents (33). Exactly how to effectively maximize engagement with mealtime insulin dosing behavior among adolescents with T1D represents a critical gap in knowledge.

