## **5.0 Study Intervention**

To identify an at-risk population for more intensive intervention opportunities, the Children's Mercy Diabetes Center now routinely uses a validated prediction model based on advanced machine learning (random forest method) and natural language processing to identify individuals who are predicted to experience a rise in A1C in the next 90 days. The model analyzes all patients who presented for a diabetes visit in the prior week. To accomplish this task, the complete health record for the CMH Diabetes Center registry is analyzed. We will select patients from this cohort for recruitment into the present study.

**COIN2DOSE intervention:** From one-week post-randomization to the 12-week study visit, youth randomized to this treatment arm will receive personalized feedback via monetary incentives for dosing insulin at mealtimes. We will define mealtimes based on hour of the day and the presence of a carbohydrate entry associated with the insulin bolus. According to the methodology for calculating BOLUS(1) breakfast will be 0600-1000, lunch will be 1100-1500, and dinner will be 1600-2200. Thus, we will reimburse youth up to \$0.50 per mealtime with at least one meal-associated (carbohydrate-associated) insulin bolus completed (maximum \$1.50/day). We will offer the opportunity for youth to earn a bonus reimbursement of up to \$5.00/week for weeks during which they achieve at least 5 days of 3 mealtime insulin boluses. Finally, we will pay youth up to \$2.00 per week for sharing their insulin use data at least two times per week with the study team during the three-month treatment phase (maximum \$24.00). Therefore, maximum total incentive available is \$210.

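### Eligibility ignores baseline mealtime bolusing, and the analysis does not fix visit 1 BOLUS as a covariate, so a ceiling could weaken the A1C and BOLUS effects carried forward

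*Protocol*

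**What the plan says.** Section 2.1 of the protocol gives the reason for the trial: "omission of mealtime boluses is one of the common reasons for suboptimal diabetes control in youth". Section 5.0 pays (COIN2DOSE) or deducts (LOAN2DOSE) $0.50 per mealtime window, $5.00 a week "for weeks during which they achieve at least 5 days of 3 mealtime insulin boluses" (or for failing to), and $2.00 a week for sharing data, to a maximum of $210.

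Section 11.0 lists six inclusion and four exclusion criteria. Two matter here:

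- Criterion 4, on the device: "The youth must be using an insulin delivery device capable of recording, storing, and downloading insulin bolus behaviors".
- Criterion 5, on glycaemia: "The youth must have a current A1C >7.2% and/or be predicted to have a rise in A1C in of 0.3% or higher".

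No criterion refers to missed boluses or to a baseline BOLUS score.

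Table 1 (Section 10.0) schedules a pump or pen download at visit 1, and change in BOLUS from visit 1 is secondary outcome 6 in Section 4.0. The covariates listed in Section 4.0 are age, sex, race, diabetes duration and depression. Section 20.2 names adherence as one of two primary predictors in a model that also contains treatment group, without saying when adherence is measured.

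**The concern.** Criterion 4 secures a bolus record that eligibility then does not use. By the figures in Section 3.1, criterion 5 does not fill the gap: "those who consistently took meal-time insulin had a significantly lower A1C of 7.8-8.0" per cent, which is above the 7.2% threshold. A youth who rarely misses a bolus can therefore be randomised, and collects or keeps most of the money without changing.

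Section 3.2 says the pilot is to look for a preliminary trend and to supply power calculations for a definitive trial. If a material share of the sample has little room to change, both the A1C and the BOLUS effects are pulled towards zero and the next trial is planned on the weaker figure. At the target of 36, each arm has 12 youth, so a few such participants, or a chance imbalance between arms in baseline dosing, would carry weight.

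The undated adherence predictor adds a second problem. If it is measured after randomisation, it conditions on the behaviour the incentives are meant to change and can remove part of the treatment effect from the group coefficient.

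**Working it through.** **Inputs from the protocol.** Three mealtime windows a day, so 21 a week; $0.50 each; $5.00 weekly bonus for at least 5 full days; $2.00 weekly for data sharing; 12 weeks (Section 5.0). Average omission: "Adolescents, on average, miss boluses for meals two times per week" (Section 3.1). A1C falls by 1.5 points per extra daily bolus, from observational data (Section 3.2).

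**The plan's own figure.** 12 × (21 × $0.50 + $5.00 + $2.00) = 12 × $17.50 = $210. It reproduces.

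**Payment with no change in behaviour, fixed number of misses each week.** This assumes the data-sharing payment is earned and each bolus has a carbohydrate entry.

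- 0 misses: $210 (100%).
- 1 miss: 12 × (20 × $0.50 + $5 + $2) = $204 (97%).
- 2 misses: at most two days are affected, so at least 5 full days remain and the bonus is earned. 12 × (19 × $0.50 + $5 + $2) = 12 × $16.50 = $198 (94%).
- 3 misses on three different days: 4 full days, no bonus. 18 × $0.50 + $0 + $2 = $11 of $17.50 a week (63%).

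The LOAN2DOSE deductions mirror these amounts.

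**Payment with random misses.** Let p be the chance of missing any window, independently. A day is full with probability (1 − p)³, and the bonus probability is binomial (at least 5 of 7 days). Expected pay = 12 × (21 × (1 − p) × $0.50 + $5 × P(bonus) + $2).

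| p | P(bonus) | Expected pay | Share of $210 |
|---|---|---|---|
| 0.095 (2 of 21) | 0.737 | $182 | 87% |
| 0.15 | 0.451 | $158 | 75% |
| 0.30 | 0.051 | $115 | 55% |

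**Room to improve.** Two misses a week is 2/7 = 0.29 boluses a day. If every miss were eliminated, the protocol's own slope gives 1.5 × 2/7 = 0.43 A1C points.

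**Attenuation, under assumption only.** If a share q of youth could show no effect at all, the mean effect scales by (1 − q) and the required sample by 1/(1 − q)². That gives 1.23 at q = 0.1, 1.56 at q = 0.2, 2.25 at q = 1/3 and 4.0 at q = 1/2. No value of q is given in the documents or can be derived from them.

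**The case against.** The strongest reply is that participants are chosen because they are expected to worsen, and Hypotheses 1 and 5 concern a smaller rise in A1C. A youth who doses well now could still benefit by not lapsing, and LOAN2DOSE rewards keeping a balance. That stands: little room at entry is not the same as no possible effect, so the (1 − q) factor is not established.

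Other points also stand in whole or part:

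- A1C and predicted rise partly select for omission. Section 3.1 gives A1C of 8.8-9.5% for youth omitting insulin at least weekly, and Section 11.0 says those approached are predicted to rise. Criterion 5 still admits youth on A1C alone.
- Two misses a week describes adolescents generally and sits at the edge of the bonus rule. Section 3.1 also reports that "greater than 33% of adolescents fail to give insulin for >15% of their meals and snacks", so many youth have more room.
- The 0.43-point possible gain exceeds the 0.3% predicted rise used to define the target group.
- Scored windows are not the same as meals. Skipped meals, or boluses without a carbohydrate entry, earn nothing.
- Broad entry is a legitimate choice in a pilot, and covariate lists are often left to a statistical analysis plan, which is not shown. But Section 20.2 already fixes a predictor list, and its adherence term is undated.

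A reader might infer that a null result could not separate a weak incentive from an untreatable sample. The documents do not support that: visit 1 downloads and the planned BOLUS outcome would reveal a ceiling. Nor do they support a claim that the trial needs 2.25 or 4 times the sample, because those multipliers rest on an assumed share.

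**Conclusion.** The point holds in a limited form. Eligibility does not use bolus behaviour, consistent dosers can enter by the protocol's own figures, and payment takes no account of where a youth starts. At the quoted average omission rate, 87% to 94% of the money is earned without change, depending on whether misses are random or steady; at 15% and 30% random omission it is 75% and 55%. These figures assume data sharing is paid and that missed meal boluses correspond to the scored windows.

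Some attenuation of the A1C and BOLUS effects is plausible, but its size cannot be computed from the documents. The clear defect is in the analysis: baseline BOLUS is collected but not named as a covariate, and the adherence predictor in Section 20.2 could be read as a post-randomisation measure.

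**What to change.** In Sections 20.1 and 20.2:

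1. Name visit 1 BOLUS, computed from the Table 1 download over a fixed period before randomisation, as a baseline covariate in the A1C and BOLUS models.
2. State that the adherence predictor in the treatment-effect model is this baseline value. Any analysis using adherence measured after randomisation should be kept separate and labelled exploratory.
3. Report the arm effect descriptively by baseline BOLUS, with no claim of a subgroup test at this sample size.

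This uses data already collected and costs one model term, or none if it takes the place of the undated adherence term.

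A bolus-based entry criterion is optional, for the sponsor here or for the definitive trial; the protocol's own mark of 5 full days a week is one candidate. It would narrow the population, and it needs a screen before randomisation, because Table 1 places consent, download and randomisation together at visit 1. Section 11.0 reports at least 81 eligible youth seen in one month; if an assumed third passed the screen, about 27 a month would remain (81 × 1/3), before refusals, against a target of 36.

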## 12.0 Vulnerable Populations

This study will include children. Parent/LAR permission will be sought before a child may be enrolled. Written assent of children 7 and older will be obtained per CMH policy; all children in this study will be above the age of assent and therefore required to assent for participation.

If a child subject reaches the age of majority (18 years old) during the study, he or she will be asked to consent to further participation using an Adult Addendum.

Parents or legal guardians of youth who are eligible to participate in this study will be eligible to participate in a focus group. It is possible that a parent or legal guardian will be pregnant at the time of focus group participation.

We will not enroll other vulnerable populations, i.e. prisoners, neonates, and/or adults lacking capacity.

Children's Mercy Kansas City employees or children of employees will not be recruited.

## 13.0 Local Number of Subjects

Target sample size is 36 adolescents. The maximum number of subjects enrolled will be 72.

Parents or legal guardians of youth eligible for inclusion in the study may choose to participate in a focus group. We may enroll up to 30 parents or legal guardians.

## **14.0 Screening and Recruitment Methods**

Patients will be prescreened to see if they meet enrollment criteria by a member of the research team. Patients who appear to meet criteria may be contacted by telephone, email or approached during a standard of care visit by a study team member and informed about this study. Patients and their parent/legal guardian will be given information about the study and they will determine if they wish to participate. Recruitment will also take place via telephone utilizing an IRB-approved telephone script.

Flyers will be used as a means of advertising the study to help with recruitment. IRB approved flyers will be used to advertise via email invitation and at all CMH locations. Recruitment will then be in person or via phone call. A copy of the flyer is attached to the submission.

Parents/legal guardians of children who meet enrollment criteria and are approached for the study will be invited to participate in a focus group at the end of the study. Recruitment for the parent/legal guardian focus group participation will occur at the same time and using the same method for recruiting the pediatric patient (i.e. by telephone or in person).

Prescreening may involve either a review of clinic schedules or a report generated by IT that will involve a review of the electronic medical record (EMR) system to generate a list of potentially eligible participants.

A HIPAA waiver is requested for the purpose of generating a pre-screening list of qualified candidates for research recruitment as described above. Information collected to track recruitment will be included in the pre-screening log for determining and tracking eligibility and tracking clinic visits where participants may be approached about the study. PHI on non-participants will be kept until completion of enrollment. Upon the completion of enrollment, the study team will also request a de-identified, aggregate report containing demographic information on individuals who declined enrollment. This information will be used to compare recruited individuals to non-recruited individuals in dissemination work products (e.g., manuscripts, presentations) so that any biases in sampling the eligible population can be reported.

## **15.0 Reimbursement, Payment and Tangible Property provided to subjects**

Participants in all groups will be compensated a total of \$120 for their time and participation. They will receive \$40 for study visit attendance and questionnaire completion. The 40 participants will each participate in 3 visits. It is possible that we may need to enroll additional participants if subjects withdraw, therefore additional funds for stipends for 4 additional subjects have been added.

Participants in the COIN2DOSE arm may earn up to an additional \$210 as incentive for completing mealtime insulin doses; the incentive payment is the intervention in this case. The total compensation for this group would be \$330.

Participants in the LOAN2DOSE arm will begin the study with a virtual bank balance of \$210 and will keep this amount if mealtime boluses and data sharing are completed as study activities are scheduled. They will also receive \$40 for study visit attendance and questionnaire completion. The total compensation for this group could be \$330.

Youth who are enrolled in the study and who elect to participate in a focus group discussion will receive an additional \$35 for doing this.

Parents/legal guardians who participate will also receive \$35 for participating.

## **16.0 Withdrawal of Subjects**

Participants may withdraw from the study at any time and this will not affect their medical care. No additional study related data will be collected on participants after withdrawal from the study, but previously collected information will be retained. All participants who enroll into the study will be included in the primary analysis, with the exception of those who are withdrawn from the study for not meeting eligibility criteria.

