## 4.0 Study Endpoints

### Outcome Measures

Primary outcome:

- 1) Change in A1C ( $\Delta A1C_{90\text{-day}}$ ) from baseline visit (visit 1) to 90-day visit (visit 2).

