## **7.0 Data and Specimen Banking**

#### Data Collection

Demographic data: Demographic data will be collected from the participant via an electronic data collection form in REDCap which shall serve as the source.

Demographic data will be verified with review of electronic medical record data. For remote visits, a web URL linking to the REDCap survey will be shared with participants.

A1C data: Participants will use a capillary A1C kit to collect a fingerstick A1C sample. An educational document and video (YouTube <https://youtu.be/e9loR3N4Rho>) have been created to educate approved study staff and participants on collection of the sample. The A1C is analyzed in a CMH lab by automated high performance liquid chromatography (reference range 4.0-6.0%, Tosoh 2.2, Tosoh Corporation, San Francisco, CA), which is a measurement method reliable to DCCT standards. The CMH A1C mail-in kit has excellent reliability to fresh samples ( $r=0.98$ ). Samples will be delivered to the Broadway lab by approved study staff for in-person study visits; samples will be mailed to the Broadway lab by participants completing remote visits from home. Sample tubes will be pre-labeled by study staff with the participant's study ID. If insufficient sample for analysis is collected at any time point, participants may be asked to repeat the sample collection to rescue data collection.

If participant does not return A1C mail-in-kit, point-of-care A1C or serum A1C may be used instead if available.

CGM data: Participants will use the Dexcom G6 Pro in blinded mode for data collection purposes only. If insufficient data for analysis are collected at any time point, participants may be asked to replace the CGM device to rescue data collection. No treatment decisions will be based on G6 Pro data. Dexcom G6 Pro data will be uploaded from the Dexcom receiver to Dexcom Clarity using the participant's personal, CMH-connected Dexcom Clarity account; data will then be collected as a .csv file for analysis. Files will be aggregated into a study database using MS Excel or equivalent software. Participants with their own CGM will use it as usual. They will be asked to share their CGM information with the study team per the usual procedure for diabetes clinic visits.

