## 20.0 Data Management and Confidentiality

### 20.1 Statistical Analysis Plan

Database construction and management will involve acquisition of data from each source (see above), imported into Microsoft Excel or an equivalent database program. All analysis will be completed using Stata/SE 15.1 (StataCorp. 2017. Stata Statistical Software: Release 15. College Station, TX: StataCorp LLC), SPSS version 20, SAS version 9.4, other statistical programs as needed. Univariate analysis will be performed on all dependent and independent variables. Analysis includes determining whether the variables have non-normal distributions or outliers. Determinations then will be made as to whether the data transformations are needed. For example, if variance heteroscedasticity, exists, data will be analyzed using log-transformed or other transformations based upon Box-Cox approximations to normal distributions. Measures of other central dependency and dispersion will be evaluated. Primary analyses will be modified intention to treat analysis. All individuals who are randomized will be included in the analysis. A secondary per-protocol analysis may also be performed. Multivariable regression models will be examined to estimate the effects of study variables on the primary outcome – predicted trajectory of glycemic control base on A1C over 90 days – for this sample of T1D patients' data collected at three time points: baseline, 3 months, and 6 months. If the independent variables are highly correlated, we will explore General Linear Models (GLM) or other models. It is possible that Generalized Estimating

Equations (GEE) will be explored for their appropriateness in a larger study and/or for comparisons with the GLM results. Demographic and clinical variables will be entered into models following the independent variable: treatment group assignment. Since time effects may be important in the analyses due to treatments, censoring of data, time sequences, or other reasons, time of observation (i.e. visit 1[day 0], visit 2 [day 90], or visit 3 [day 180]) will also be explicitly accounted for in the regression models. All models will account for the clustering effect of participants having more than one clinic visit during the study timeframe. Additional variables will be collected as listed above. Statistical significance will be  $p<0.5$  (one-sided).

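### Section 16 ends all data collection at withdrawal and does not separate stopping the incentives from leaving follow-up, so a participant who withdraws before visit 2 is analysed with baseline data only

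*Protocol*

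**What the plan says.** Section 16.0 lets participants withdraw at any time without effect on their care, and then sets the collection rule: "No additional study related data will be collected on participants after withdrawal from the study, but previously collected information will be retained". It goes on: "All participants who enroll into the study will be included in the primary analysis". The only exception is for people withdrawn because they did not meet the eligibility criteria.

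Section 20.1 names the population: "Primary analyses will be modified intention to treat analysis", and then "All individuals who are randomized will be included in the analysis". The primary outcome in Section 4.0 is the A1C change between visit 1 and the 90-day visit 2.

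Two other places bear on whether a day-90 value could be had. Section 7.0, under A1C data, says that if the mail-in kit does not come back, "point-of-care A1C or serum A1C may be used instead if available". Section 4.0, under Covariate Measures, puts clinic encounters at typically 3 to 4 months apart.

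The protocol describes one exit, withdrawal from the study. It does not say what happens to a participant who wants to give up the incentives or the uploads but is willing to be followed.

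**The concern.** An analysis of everyone randomised is only as good as the outcomes collected. Section 16.0 keeps withdrawn participants in the analysis set but closes the route by which their primary outcome could be observed.

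The burden that might prompt withdrawal is unequal by design. The footnote to Table 1 in Section 10.0 asks for pump or pen uploads twice weekly in COIN2DOSE and LOAN2DOSE, but monthly in control, and Section 6.0 describes the trial as unblinded. If those who leave have a different A1C course from those who stay, or leave at different rates by arm, the observed day-90 values no longer compare the groups as randomised. Section 3.2 says the pilot's data will feed power calculations for a definitive trial, so a distorted estimate would carry forward.

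This is a protocol matter. A statistical analysis plan can say how missing values are modelled, but it cannot supply an A1C that the protocol says will not be collected.

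**Working it through.** The plan gives no dropout rate and no figure for missing day-90 A1C, so there is no stated value to reproduce. The check has two parts.

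**1. The passages side by side, for a participant who withdraws between visit 1 and visit 2**

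- In the primary analysis? Yes (Sections 16.0 and 20.1), unless ineligible.
- Study A1C at visit 2? No (Section 16.0).
- Baseline A1C kept? Yes (Section 16.0).
- Clinic A1C possible? Yes, since care continues. The visit-2 window in Table 1 is 3 months ± 14 days, that is days 90 − 14 = 76 to 90 + 14 = 104. Encounters 3 to 4 months apart fall at about days 90 to 120, so some fall inside the window and some outside.
- May that clinic value be used? Not under Section 16.0 as written. For a participant still enrolled whose kit is missing, Section 7.0 allows it.

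**2. Size, under stated assumptions**

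Let p be the fraction of an arm without a day-90 A1C, and d the difference in mean A1C change between those lost and those observed. The full-arm mean is (1 − p) × observed mean + p × (observed mean + d), so the observed mean differs from it by p × d.

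Range for p (assumed):

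- Lower end, 10%: the stipend budget in Section 15.0 allows 4 extra participants on 40, and 4/40 = 10%.
- Upper end, 25%: Hypotheses 9 and 10 in Section 2.2 tolerate up to 25% not completing all procedures. This is broader than withdrawal, so 25% is an upper illustration and not a forecast.

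Range for d (assumed; the protocol gives no basis): 0.5 to 1.0 A1C points, in either direction.

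| p | d = 0.5 | d = 1.0 |
|---|---|---|
| 10% | 0.10 × 0.5 = 0.05 | 0.10 × 1.0 = 0.10 |
| 25% | 0.25 × 0.5 = 0.125 | 0.25 × 1.0 = 0.25 |

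At the target of 36 (12 per arm), 25% is 0.25 × 12 = 3 participants. At the maximum of 72 (24 per arm), it is 0.25 × 24 = 6.

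The error in the between-arm difference is p₁d₁ − p₀d₀, with subscript 1 for the intervention arm and 0 for control. If both arms lose the same fraction with the same d, it is zero. If an intervention arm loses 25% and control 10% with a common d, it is 0.125 − 0.05 = 0.075 points for d = 0.5, and 0.25 − 0.10 = 0.15 points for d = 1.0. If control loses more, the sign reverses.

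**The case against.** Much can be said for the plan as it stands.

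- **Ending collection at withdrawal is ordinary practice, and Section 16.0 does not strictly contradict itself.** Earlier data are kept, and Section 20.1 models A1C at baseline, 3 and 6 months with time and within-participant clustering. A baseline-only participant can enter such a model, and the handling of missing data may be in a statistical analysis plan that is not shown. This stands, so it would be too strong to say that the all-enrolled rule cannot be met. But a baseline value adds little about day 90, and the model then relies on assumptions about the unseen values.
- **Non-engagement is not withdrawal.** A reader might infer that anyone who tires of uploading must leave the study. The documents do not support that: under Section 5.0 a non-uploader forgoes or loses up to $2 a week and remains enrolled, and Section 7.0 still allows a clinic A1C. The gap is confined to formal withdrawal.
- **An exhausted LOAN2DOSE balance is not a likely trigger.** Maximum weekly loss is 7 × $1.50 + $5 + $2 = $17.50, so $210 lasts 210/17.50 = 12 weeks even if every dose and upload is missed.
- **The budget line for extra participants is not an analysis rule.** Section 15.0 says "It is possible that we may need to enroll additional participants if subjects withdraw". A reader might take this as replacing those who leave, but Section 16.0 already keeps the withdrawn in the analysis.
- **The 25% is not a rate of A1C loss.** A participant who misses one questionnaire fails the completion criterion and can still have a day-90 A1C. This stands, and 25% is used above only as an upper bound for illustration.
- **The consent pages are not in the copy reviewed.** They may already give a permission for later record use. That cannot be checked, but Section 16.0 as worded would still bar using it.

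**Conclusion.** The point holds in a limited form. The protocol stops collection at withdrawal, does not distinguish stopping the incentives or uploads from leaving follow-up, and so gives up day-90 A1C values that may exist in a source it already accepts. Under the assumed 10% to 25% loss and 0.5 to 1.0 point difference, one arm's mean shifts by 0.05 to 0.25 A1C points. The effect on the between-arm difference depends on how far loss differs by arm, and could be nil.

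Two stronger conclusions are not supported. One is that the loss would favour the interventions: controls receive no incentive and might leave more often, so the direction is unknown. The other is that withdrawn participants have no safety follow-up: usual care continues, the study is rated minimal risk, and Section 21.0 provides for a monitoring board that reviews adverse events. What ends is study-collected data.

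This is an inexpensive improvement and worth making. It is not an error that invalidates the design.

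**What to change.** In Section 16.0:

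1. State that a participant who stops only the incentives or the uploads remains in follow-up for visits 2 and 3.
2. Offer those leaving the study the option, by permission in the consent form, of having the routine clinic A1C nearest day 90 and day 180 taken from the health record, within the ± 14-day visit windows.
3. State that collection stops fully only if that permission is also withdrawn.

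This concerns data collection only and sets no rule on when anyone should stop the intervention.

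The cost is rewording of the protocol and consent form and a small chart review. The downside is that some A1C values will come from clinic assays, a source Section 7.0 already accepts, and some participants will have no value within the window.
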